3.4 Outcomes

COVID-19 vaccine effectiveness studies

The outcome of interest for the primary analysis is SARS-CoV-2 infection in patients of all ages hospitalised with SARI symptoms, laboratory-confirmed by PCR, documented either on admission to hospital or in the 14 days before admission.

Secondary outcomes of interest, in the same patient group, are laboratory-confirmed infections with genetic variants of SARS-CoV-2 and confirmed SARS-CoV-2 patients with severe outcomes (ICU admission, invasive ventilation or death).

Influenza vaccine effectiveness studies

The outcome of interest is laboratory-confirmed influenza in patients of all ages, hospitalised with SARI symptoms.

More specifically, this will be:

- subtype-specific laboratory-confirmed influenza A;
- laboratory-confirmed influenza B overall and, if available, by lineage (B Victoria/B Yamagata);
- laboratory-confirmed influenza by clade (where possible);
- laboratory-confirmed influenza co-infected with SARS-CoV-2 (where possible).

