3.5.3 SARI patients confirmed as COVID-19

A confirmed COVID-19 case will be defined as a hospitalised patient fulfilling the SARI case definition, with a respiratory sample positive for SARS-CoV-2 by PCR, [29] either on admission to hospital or documented in the 14 days prior to hospital admission.

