3.5.5 SARI patients testing negative for SARS-CoV-2/influenza (test-negative controls)

A control will be defined as a hospitalised patient fulfilling the SARI case definition, with a respiratory sample negative for SARS-CoV-2 by PCR (for CVE) or a respiratory sample negative for influenza (for IVE) on admission to hospital.

It is advised that all sites test for both SARS-CoV-2 and influenza during the influenza season, as well as for all other respiratory viruses (as appropriate, depending on time of year), even if they are not participating in IVE. If this is not feasible, then during influenza season all samples that are negative for SARS-CoV-2 should also be tested for influenza (if not already tested at primary care level).

Controls that are negative by PCR but have Ct results suggestive of COVID-19⁶, and those with prior SARS-CoV-2 infection in the three months before admission, may be excluded as controls in sensitivity analyses (see Section 3.5.7 'Exclusion criteria').

- A study site/country measuring only CVE should indicate which testing strategy they will use (testing all samples for both SARS-CoV-2 and influenza, or only testing for influenza in those negative for SARS-CoV-2).
- > Each study site/country to indicate whether they can test for other respiratory viruses, only SARS-CoV-2 and influenza, or only SARS-CoV-2.

Other control groups (optional)

During periods when respiratory viruses are in low circulation, the number of SARI patients testing negative for SARS-CoV-2/influenza may be limited. Some sites may therefore wish to include other control groups, either in addition to SARI controls or as an alternative, and these must be recruited throughout the whole study period.

Examples of other control groups include:

- Patients testing PCR-negative to all respiratory viruses;
- Patients testing PCR-positive to respiratory viruses other than influenza (if IVE) or SARS-CoV-2, e.g. rhinovirus, respiratory syncytial virus (RSV), etc.; noting that patients with seasonal coronaviruses are excluded for CVE;
- Patients hospitalised with non-SARI related symptoms matched by time, age group and, if possible, underlying conditions:
 - Example source of hospitalised non-SARI cases: hospital wards admitting patients without COVID-19.
 Primary care: selection of GP patients belonging to the hospital catchment area and vaccination target
- group matched by time and age group:

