3.5.6 Exclusion criteria

The patient will not be enrolled in the study if she/he:

- is unwilling to participate or unable to communicate and give consent (the consent may also be given by her/his legal representative, or by specific consent procedures, acceptable according to the local ethical review process);
- has a contraindication for the COVID-19 (for CVE) or influenza (for IVE) vaccination;
- cannot be swabbed due to severe septum deviation, obstruction or other conditions that contra-indicate swabbing:
- has a history of hospitalisation within the 14 days immediately prior to this admission (including transfers from another hospital);
- had his/her SARI onset ≥ 48 hours after admission to the hospital (for IVE) or ≥ 7 days after admission to the hospital (for CVE);
- was institutionalised at the time of symptom onset (lives at a care-home/residence for people who require
 continual nursing care and have difficulty with the required activities of daily living);
- had a respiratory specimen taken ≥ 8 days after SARI symptom onset (for IVE) or ≥ 10 days after SARI symptom onset (for CVE);
- had a respiratory sample taken ≤ 3 days before SARI symptom onset (for CVE)
- tested positive for any influenza virus in the current season before the onset of symptoms leading to the current hospitalisation (IVE).

Information will be collected on these and other potential exclusion factors and patients will be excluded from primary analyses according to available evidence on these factors (not all available at time of writing).

In sensitivity analyses, the CVE/IVE will be estimated:

- with different cut-offs for numbers of days between onset and swabbing, onset and hospitalisation, and between vaccination and onset of symptoms;
- excluding those positive for seasonal coronaviruses (e.g. HCoV-NL63, HCoV-229E, HCoV-OC43 and HCoV-HKU1):
- excluding those who are current controls (SARS-CoV-2 negative for CVE; influenza negative for IVE) but were
 positive by PCR in the previous year before the current hospitalisation, or reported clinically confirmed COVID19, so as to determine the best cut-off period for having had a previous positive test during the preceding
 year versus 'any previous positive test' irrespective of date;
- using results from rapid antigen tests (RATs) when PCR information unavailable;
- dropping SARS-CoV-2-positive controls from IVE analysis and dropping influenza-positive controls from CVE analysis;

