3.9.9 Previous SARS-CoV-2/influenza infection

Individuals who have been previously infected may have a greater response to the vaccine or be less likely to be reinfected, even if unvaccinated. Previous infection may impact the probability of receiving a COVID-19 vaccine (e.g. if the perception of risks associated with a new SARS-CoV-2 infection differs by previous infection status) and the risk of infection (due to immunity conferred by past exposure to SARS-CoV-2) [28]. Therefore, confounding of CVE by previous infection status may arise. Previous infection status may also be an effect modifier, as COVID-19 vaccination may provide greater absolute benefit to people without pre-existing immunity [29].

If possible, study sites will collect the following information:

- whether the patient had a previous positive SARS-CoV-2 test(s) (yes/no/unknown)
- optional:
 - type(s) of test: PCR, rapid test (in case of multiple positive test results, the most recent)
 - date(s) of test (in case of multiple positive test results, the most recent)
 - history of COVID-19, e.g., clinical confirmation.

If all study sites collect information on previous SARS-CoV-2 infection, the following analyses will be conducted with the pooled data. Otherwise, these analyses will be conducted in the subset of sites that collect this information. In the primary analysis, patients testing SARS-CoV-2 positive in the previous 60 days will be excluded from the analysis (this will avoid including cases who test positive due to prolonged shedding of a given illness episode and avoid including controls who are not at risk of being a case, according to the ECDC reinfection definition) [28]. Separate sensitivity analyses could be carried out including controls who recently tested SARS-CoV-2 positive, adjusting CVE estimates for previous SARS-CoV-2 infection, or stratifying CVE estimates by previous SARS-CoV-2 infection, if sample size allows. Additionally, if sample size allows and information is available, controls previously infected with SARS-CoV-2 will be included or excluded depending on number of days since last infection (to be explored in sensitivity analyses), or variant of infection.

Each study site/country to collect and describe measure(s) used to capture prior SARS-CoV-2/influenza infection.

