3.13.2 Sensitivity analyses

As sensitivity analyses, study sites can measure CVE/IVE:

- with different cut-offs of numbers of days between onset and swab;
- with different cut-offs of numbers of days between vaccination and symptom onset;
- with varying the post-vaccination periods (e.g. 7 days, 14 days, etc.) to be considered 'completely vaccinated' or 'partially vaccinated' (see Section 3.8.1);
- including, excluding, stratifying or adjusting by previous positive test status, and also by different delays between prior test and inclusion in the study:
- excluding patients testing positive prior to hospitalisation but negative in hospital;
- · using only controls positive to other respiratory viruses;
- excluding controls testing SARS-CoV-2 positive (IVE) or influenza positive (CVE), or adjusting by COVID-19 vaccination (see also Section 5.1.7);
- using different reference groups for VE estimation (e.g. for CVE: unvaccinated people, people vaccinated with a smaller number of doses, people vaccinated in the previous season).
- 3.13.3 Pooled analysis.

The higher sample size for the pooled analysis will provide more precision around the VE estimates. Data can be coded as outlined in Annex 1, or a codebook can be provided by the study teams that includes the variable names, descriptions and coding. The central hub will perform data cleaning and document and share any further data cleaning and analysis with all study coordinators to ensure it can be reproduced.

See Annex 2 for details of the pooled analysis plan. For the pooled data, interim analyses will be conducted during different periods, if appropriate, and according to the available sample size.

The timing to conduct each interim analysis will depend on the time needed to achieve the appropriate sample size. This will depend mainly on the incidence of hospitalisation, COVID-19/influenza incidence, vaccination coverage, the recruitment strategy within hospitals and the number of participating hospitals/services per hospital.

The pooled analysis will be carried out in a similar way to the site-specific analysis. Country or study site will potentially be included as a fixed effect, or as a random effect in a multi-level model. Statistical heterogeneity between study sites will be determined in a two-stage analysis using the Q-test and the I² index [30].

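### The 60-day exclusion for earlier SARS-CoV-2 positives conflicts with the 14-day pre-admission case window, and a patient positive before but negative on admission fits both the case and the control definition

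*Protocol*

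**What the plan says.** - **Case.** The primary outcome (Protocol 3.4) is PCR-confirmed infection "documented either on admission to hospital or in the 14 days before admission". The case definition (3.5.3) uses the same window: "either on admission to hospital or documented in the 14 days prior to hospital admission".
- **Control.** Section 3.5.5 asks for a SARI patient with a PCR negative for SARS-CoV-2 (for CVE) or "a respiratory sample negative for influenza (for IVE) on admission to hospital". It sets no condition on an earlier positive test.
- **Primary-analysis exclusion.** Section 3.9.9: "In the primary analysis, patients testing SARS-CoV-2 positive in the previous 60 days will be excluded from the analysis". Two reasons follow: "this will avoid including cases who test positive due to prolonged shedding of a given illness episode", and to "avoid including controls who are not at risk of being a case". The exclusion list in 3.5.6 does not contain this rule.
- **Positive, then negative.** Section 3.13.2 lets sites run a sensitivity analysis "excluding patients testing positive prior to hospitalisation but negative in hospital".
- **Other look-backs, all sensitivity analyses.** Section 3.5.5 allows removal of controls infected in the preceding three months. Section 3.5.6 proposes "excluding those who are current controls (SARS-CoV-2 negative for CVE; influenza negative for IVE) but were" PCR-positive in the previous year, in order to settle on a best cut-off. Section 5.1.5 removes any SARI patient with an earlier PCR-confirmed infection.
- **Data.** Section 3.9.9 lists the date of the earlier positive test as optional and, where there are several, keeps only the most recent. Annex 1 holds that date in Section I (tests before hospitalisation), among the variables not marked optional. Section J covers tests during hospitalisation.

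**The concern.** In a test-negative design each patient must fall into exactly one of three sets: case, control or excluded. Here the same fact, a positive PCR a few days before admission, makes a patient a case under 3.5.3 and removes that patient under 3.9.9. If the removal is not meant for such patients, those who then test negative on admission meet both 3.5.3 and 3.5.5.

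The primary dataset would therefore depend on how each site, or the central hub, reads the rule. The affected patients are those tested in the community before admission. If community testing is related to vaccination behaviour, losing or misplacing these patients may not be neutral.

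**Working it through.** **1. The rules side by side, for PCR-positive patients on day −5 (five days before admission)**

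| Patient | 3.5.3 | 3.5.5 | 3.9.9, literal | 3.9.9, earlier episodes only |
|---|---|---|---|---|
| Positive on admission too | case | no | excluded | case |
| Negative on admission | case | control | excluded | case and control |
| Not retested | case | no | excluded | case |

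Under the literal reading all three patients go, although 3.4 and 3.5.3 were written to admit them. Under the other reading the second patient has two classifications. If the date of the earlier test is missing, neither the 14-day nor the 60-day rule can be applied, and that patient would probably be filed as a control on the admission result.

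Annex 1 cannot separate the readings. The result that qualifies a pre-admission case is stored in the same prior-positive field that would trigger the exclusion. No flag marks the current episode. Because only the most recent positive is kept, a positive on day −5 also overwrites one on day −40, which is the kind of earlier episode the rule is aimed at.

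**2. Size if positive-then-negative patients are counted as controls**

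Assumptions, not in the Protocol: true CVE 50% (OR 0.5) and true control coverage 0.5. Case odds of vaccination are then 0.5 × 1 = 0.5, so case coverage is 1/3. With a share m of controls really cases, observed control coverage is c = 0.5(1 − m) + m/3, and VE = 1 − 0.5/[c/(1 − c)].

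- m = 3%: c = 0.4950, odds 0.9802, VE 49.0%
- m = 5%: c = 0.4917, odds 0.9672, VE 48.3%
- m = 10%: c = 0.4833, odds 0.9355, VE 46.6%

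The bias is downwards.

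**3. Size if the 60-day rule is applied literally**

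Start from the Table 5 row for OR 0.5, coverage 0.5 and precision 0.2: 289 cases, 289 controls, CI 30–64. SE = √[1/(289 × 2/9) + 1/(289 × 1/4)] = √(0.01557 + 0.01384) = 0.1715. The limits are 1 − 0.5·exp(±1.96 × 0.1715), giving 30.0% and 64.3%, so the table row is reproduced. Multiply the number of cases by 1 − f, where f is the assumed share confirmed before admission:

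- f = 5%: 29.7–64.4%
- f = 30%: 27.4–65.5%

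This covers precision only. It assumes that the lost cases have the same vaccine coverage as the rest.

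**4. Control-only look-backs (sensitivity analyses)**

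Assume 20% of controls were previously infected, coverage is 50% in the others, prior infection halves the odds of being a case, and the OR is 0.5 in both strata. Take coverage of 30% in the previously infected.

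- Controls, vaccinated/unvaccinated: not previously infected 0.40/0.40; previously infected 0.06/0.14.
- Cases: 0.20/0.40 and 0.015/0.07.
- No exclusion: OR = (0.215/0.47)/(0.46/0.54) = 0.537, VE 46.3%.
- Excluded from both groups: OR = (0.20/0.40)/(0.40/0.40) = 0.5, VE 50.0%.
- Excluded from controls only: OR = (0.215/0.47)/(0.40/0.40) = 0.457, VE 54.3%.

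With 60% coverage in the previously infected instead, control-only exclusion gives (0.23/0.44)/1 = 0.523, VE 47.7%.

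With 5–40% previously infected and a case-odds factor of 0.2–1.0, control-only exclusion gives 50.2–63.8% if their coverage is 30–40%, 50.0% if it is 50%, and 41.3–49.8% if it is 60%. Excluding from both groups gives 50.0% throughout.

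**The case against.** The strongest reply is that context settles the meaning of the 60-day rule. It stands in a section on previous infection, follows a list of earlier positive tests, and is justified by prolonged shedding and by a reinfection definition. The analysis in 3.13.2 that drops positive-then-negative patients would have few left to remove if the literal rule had already taken them. The intended target is therefore probably an earlier episode. That stands, and it makes the literal deletion a risk of the wording rather than the evident design. It does not rescue the text, because this reading is the one that opens the overlap between 3.5.3 and 3.5.5, and an optional sensitivity analysis does not say in which group these patients sit in the primary analysis.

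A reader might also infer that look-backs are applied to controls only and so inflate CVE. The Protocol does not support that for the primary estimate. The 60-day rule covers patients generally and gives one reason for cases and one for controls. The control-only versions are sensitivity analyses. Section 5.1.5 adds a symmetric one, section 3.13.2 allows including, excluding, stratifying or adjusting by earlier positive status, and section 3.9.9 also offers adjustment and stratification. Nor is the direction fixed: 5.1.5 says only that people who know they were infected may be less likely to be vaccinated, and the sign reverses if they are more vaccinated.

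Finally, a reader might add the two harms together. They cannot both befall the same patient: one who is deleted is neither case nor control.

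**Conclusion.** The point holds as an unresolved conflict between 3.4/3.5.3, 3.5.5 and 3.9.9 over who enters the primary CVE analysis and in which group. It should be corrected, because different analysts could build different primary datasets from the same text.

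The likely size is modest: a loss of about one to three percentage points of CVE if 3–10% of controls are really cases, or a slightly wider interval if pre-admission cases are deleted. Both figures rest on assumed shares that the Protocol does not give. Neither figure covers selective loss of cases related to vaccination.

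The control-only look-backs are a secondary matter. They can shift their own sensitivity estimates in either direction, upwards if the previously infected are less vaccinated. They matter because 3.5.6 would use such runs to choose a cut-off.

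**What to change.** - **3.9.9 (and repeat in 3.5.6):** define the index date of the 60-day rule and exempt the qualifying test of the current episode, for example by limiting the rule to positives dated 15–60 days before admission.
- **3.5.5:** add that a control for CVE has no positive SARS-CoV-2 PCR in the 14 days before admission. Positive-then-negative patients are then classified once, as cases under 3.5.3. Keep their removal (3.13.2) as a sensitivity analysis.
- **3.9.9 and Annex 1:** make the date of the earlier positive test core in 3.9.9, in line with its place in Annex 1. Since only the most recent positive is recorded, add a flag for current versus earlier episode, or a second date.
- **3.5.5 and 3.5.6 look-backs:** apply each one to cases and controls alike, as 5.1.5 does, and report all cut-offs rather than selecting a best one.

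The cost is wording in a few sections and one added variable. The downside is that symmetric look-backs remove some cases from the sensitivity analyses.

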3.9.11 Pregnancy status

Pregnancy status will be collected and coded for women aged 15–55 years as follows: pregnant (yes/no/do not know), and if yes: trimester (1/2/3/do not know).

3.9.12 Smoking history

Smoking history will be collected and coded as follows: never-smoker, former smoker (stopped smoking at least one year before inclusion in the study), current smoker (smoking currently or stopped within a year of study recruitment).

3.9.13 Healthcare worker

The definition of a healthcare worker for the purposes of this study is anyone working (paid or on a regular voluntary basis) in healthcare who has contact with any type of patient during his/her work. This includes doctors, nurses, emergency medical personnel, medical and nursing students having contact with patients, and porters and cleaners. It also includes anybody working in a nursing/residential home for the elderly who has contact with residents. Study sites should collect information on healthcare worker status where possible. Patients with known healthcare worker status will be excluded from analyses for both CVE and IVE.

> Each study site/country to indicate whether they can collect information on healthcare worker status.

3.9.14 Other occupations

As some occupations predispose individuals to greater exposure, and may be a proxy for attitudes towards vaccination, where possible, countries may collect additional information on occupation for stratification in analysis by type of occupation. Documentation of this variable remains optional.

Each study site/country to indicate whether they intend to/can also collect information on occupation in general (optional).

3.9.15 Presence of other respiratory virus infections

It is important to document the presence of influenza (for study countries not participating in IVE) and other respiratory viruses in cases and controls. Analysis will document the presence of other respiratory infections (e.g. RSV) among patients testing negative for SARS-CoV-2, and those who are positive.

> Each study site/country to list the other respiratory infection viruses that they test for (including influenza).

3.9.16 Healthcare utilisation in the previous 12 months

In order to document and control for healthcare-seeking behaviour and the severity of underlying conditions, study sites can collect:

> the number of hospital admissions due to underlying conditions in the 12 months prior to inclusion in the study.

3.12.1 Administrative information

Study identifiers

For each country/study sites, the following characteristics need to be documented:

- Country, site, priority vaccination target group(s) and their modifications;
- Hospital (unique number not including hospital name, to allow adjustment by hospital in analyses);
- Patient unique ID (note: this is not a patient identifiable ID such as date-of-birth or national ID number, but a unique identifier for a pooled database).

Hospital/ward information

The following dates and other hospital information need to be documented:

- Date of onset, admission, discharge, death;
- First ward of referral;
- Any hospital stay (for pre-existing chronic condition) in previous 12 months (optional);
- Date of swab/sample.

Data entry validation

For hospitals using electronic medical records, if paper questionnaires are used, a sample of them will be checked against the medical records and against the study database. For hospitals using electronic patient hospital records, a sample of records from the study database can be compared with the medical records. Concurrence between patient records/reports by study participants will be measured when/if records are available.

- > Each study site/country to specify how data are validated;
- > The specific validation procedures, including sample size calculation for questionnaire validation (if applicable) should be specified in the study annexes;
- Vaccination status, date, dose(s) if relevant and vaccine brand should be collected carefully and validated.

